underlying platform generates customized learning experiences for each individual user with content including videos, text, quizzes and interactive exercises. The program comprises nine lessons of 30 minute each during which the user first learns the key concepts; then applies them to the program's main character who suffers from depression; and then applies those techniques to their own personal challenges (<http://www.empower-interactive.com/solutions/good-days-ahead>). Participants are expected to complete the nine sessions over 9-12 weeks.

As patients complete the cCBT program, their progress will be monitored by the research coordinator through a secure web site, using the program's dashboard feature that includes tracking of mood ratings, exercises, comprehension and completion rates. Participants will receive guidance during regular contacts by a trained research coordinator knowledgeable about the program and the basics of CBT.

MEASUREMENT

Three types of measures are under study: (i) depressive symptoms, (ii) self-reported cognitive difficulties; (ii) cognitive performance.

(i) Depressive symptoms will be measured using the Hospital Anxiety and Depression Scale (HADS) [19] before beginning and right after cCBT completion. It comprises two 7-item scales designed to rate depression and anxiety. It was developed to be brief, non-threatening and to exclude items which might reflect somatic symptoms. It has been widely used in research [20]. A score on the depression subscale (HADS-D) ≥ 8 is indicative of the presence of depression.

(ii) Self-reported cognitive difficulties will be measured using the C3Q collected before beginning and right after cCBT completion. The C3Q is a self-report measure of cognitive difficulties comprised of 18 items covering multiple cognitive domains. For each item, individuals rate the frequency of a cognitive difficulty on a three-point scale. The items fit the Rasch model, producing a legitimate total score with mathematical properties ranging from 0-36 with lower scores indicating more severe difficulties. C3Q has good content and construct validity and a good internal reliability (Person Separation Index 0.84) [18]. The mean score of C3Q among HIV+ individuals is 26.3 (SD: 8.2).

(iii) Cognitive performance will be measured by the B-CAM, a computerized test of cognition that yields a score on a continuous metric [21]. The B-CAM is administered at the regular BHN

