The Effects of computerized Cognitive Behavior Therapy (cCBT) on Brain Health: A feasibility study

cohort visits. Two values will be used, those closest to the beginning and end of the CBT intervention period, usually 9 months apart.

STATISTICAL ANALYSIS AND SAMPLE SIZE

Basic descriptive statistics will be used to characterize the participants including values on all the outcomes.

To meet the first aim of linking change in depressive symptoms (as a result of cCBT) to change in self-reported cognitive difficulties, an analysis based on a comparison of two means will be carried out. The cCBT cohort will be classified as having changed on depressive symptoms if the score on the HADS-D has either fallen to below 8 or decreased by $\frac{1}{2}$ SD (2 points). The mean value of change on the C3Q will be compared between these two groups (depression improved vs no change), using an adjusted t-test based on linear regression, adjusted for covariates that differ between the two groups. This t-test is an estimate of between group effect size. The parameter of interest, however, is the within group effect size for cognitive change using the standardized response mean (SRM), which is the average within group change divided by the standard deviation of change. The two SRMs will be compared using relative effectiveness: SRM (depression improved group) / SRM (depression no change group)[16]. If this ratio exceeds 1.0, there is supportive evidence for a greater response in the depression improved group. This information on the between and within-effect sizes will be used to develop a fully powered study of this association.

The extent to which changes in self-reports are concordant with changes in cognitive performance will be assessed using percent agreement and 95% confidence intervals (CI). Each person will be classified as a responder or not based on change on the C3Q and on the B-CAM, with responder status defined as improvement of $\frac{1}{2}$ SD. This represents a change of 4 points on the C3Q and 2.3 points for the B-CAM. The table below shows the potential outcome patterns. If the value of c=0, all persons with decreased reports of cognitive difficulties also had improved cognitive performance with cCBT.

The Effects of computerized Cognitive Behavior Therapy (cCBT) on Brain Health: A feasibility study

		Cognitive difficulties C3Q	
		Decreased	no change
Cognitive performance B-CAM	improved	a	b
	no change	c	d

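### Raw percent agreement between two half-SD responder labels cannot, by itself, separate real concordance from chance and measurement error

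*Combined protocol and SAP*

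**What the plan says.** Under STATISTICAL ANALYSIS AND SAMPLE SIZE, responder status on both cognitive measures is an improvement of half an SD. "Each person will be classified as a responder or not based on change on the C3Q and on the B-CAM", and the cuts are given in points: "This represents a change of 4 points on the C3Q and 2.3 points for the B-CAM". Concordance "will be assessed using percent agreement and 95% confidence intervals (CI". The plan adds a reading of the 2x2 table: if cell c (C3Q improved, B-CAM not) is empty, then "all persons with decreased reports of cognitive difficulties also had improved cognitive performance with cCBT". It illustrates precision with 12 concordant people of 30, and it intends to compare the characteristics of concordant and discordant people.

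MEASUREMENT, item (ii), supplies the C3Q figures. The score is described as "ranging from 0-36 with lower scores indicating more severe difficulties", so improvement is a rise. The item reports "a good internal reliability (Person Separation Index 0.84" and states: "The mean score of C3Q among HIV+ individuals is 26.3 (SD: 8.2".

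The documents give no standard error of measurement, no test-retest reliability for the C3Q and no reliability for the B-CAM. No chance-corrected index is planned, and the single-cohort design has no untreated group to show a background responder rate.

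**The concern.** The C3Q cut is about the same size as the error of a C3Q change score, so some people will be labelled responders, or missed, through error alone. Percent agreement is then taken at face value. Two different misreadings follow. Perfect true concordance can yield only moderate agreement. Equally, agreement can look fair when nobody has changed, because two mostly negative labels agree often by chance.

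The BACKGROUND section says that the clinical importance of self-reported difficulties is uncertain when testing is normal, and this comparison bears on that question. The same misclassification carries into the planned contrast of concordant and discordant people, since some of the discordant would be so only through error.

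**Working it through.** **Inputs from the protocol.** C3Q SD 8.2; Person Separation Index 0.84; cuts of 4 points (C3Q) and 2.3 points (B-CAM); 30 people analysed. The B-CAM cut implies an SD of 2 × 2.3 = 4.6.

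**The plan's own figures.** 0.5 × 8.2 = 4.1, rounded to 4, so the cut reproduces. For 12/30 the Wilson interval is 0.246 to 0.577, which matches the printed 0.25 to 0.58. That interval covers sampling error only.

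**Error of a C3Q change** (0.84 taken as the reliability of each score, normal independent errors):
- SE of one score = 8.2 × √(1 − 0.84) = 3.28
- SE of a change = 3.28 × √2 = 4.64
- cut / SE = 4 / 4.64 = 0.86
- P(unchanged person gains ≥ 4) = 1 − Φ(0.86) = 0.194, or 30 × 0.194 = 5.8 people if all 30 were unchanged

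**Sensitivity to the SD, reliability held at 0.84.**

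| SD | SE of change | False-responder rate | Expected among 30 unchanged |
|---|---|---|---|
| 6 | 3.39 | 0.119 | 3.6 |
| 7 | 3.96 | 0.156 | 4.7 |
| 8.2 | 4.64 | 0.194 | 5.8 |

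If instead the SE of one score stays at 3.28 in a narrower sample, the rate stays at 0.194.

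**Two opposite truths, same expected agreement.** Assume B-CAM reliability 0.84 (not stated) and unrelated errors. SE of a B-CAM change = 4.6 × √0.32 = 2.60; false-responder rate = 1 − Φ(2.3/2.60) = 0.188.
- Nobody changes: agreement = 0.806 × 0.812 + 0.194 × 0.188 = 0.69. Kappa and correlation are 0.
- 40% improve by 1 SD on both measures, the rest on neither. Response probabilities among improvers are 0.817 (C3Q) and 0.812 (B-CAM), so they agree with probability 0.817 × 0.812 + 0.183 × 0.188 = 0.698. Overall agreement = 0.6 × 0.691 + 0.4 × 0.698 = 0.69.
- In the second case the marginal responder rates are 0.444 and 0.438, chance agreement is 0.444 × 0.438 + 0.556 × 0.562 = 0.507, and kappa = (0.693 − 0.507) / 0.493 = 0.38. The correlation of changes, in SD units, is 0.24 / (0.24 + 0.32) = 0.43, where 0.24 = 0.4 × 0.6.

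**The c = 0 reading.** Assume 18 of 30 truly unchanged, the other 12 truly improved on both, and an error-free B-CAM. Cell c then holds only C3Q false responders: 18 × 0.194 = 3.5 expected, and P(c = 0) = 0.806^18 = 0.02. With SD 7 or 6 and reliability 0.84, P(c = 0) is 0.844^18 = 0.05 or 0.881^18 = 0.10.

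**The case against.** The case for leaving the plan alone has several parts.

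- **The hypothesis is categorical.** STUDY HYPOTHESIS says that those who do not improve on self-report will not improve on performance, and that those who do will. The 2x2 table answers that directly; a correlation does not. This stands, and it is why the table should stay.
- **The inputs may not fit this sample.** The SD is for HIV+ people in general, while participants are selected on HADS-D ≥ 8 and PDQ ≥ 30. The index is internal, and the documents do not show that it and the SD come from one sample. This stands in part. At SD 6-7 with reliability held, the SE of change drops below 4 points and the rate is 12-16%. On the other side, an internal index leaves out occasion-to-occasion variation, so the true error is more likely larger than smaller.
- **The alternatives suffer from the same error.** With an error-free B-CAM, 40% true responders gaining 8 points and perfect concordance, agreement is 0.81 but kappa is only 0.60 and the correlation 0.65. This stands. Neither is a cure, though both are 0 when nothing changes, which raw agreement is not.
- **Stakes are low.** It is a secondary, exploratory question in a feasibility study with no decision threshold. This also stands.

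A reader might infer more than the documents support. One inference is that agreement has a hard ceiling: the limit is on expected agreement, not on any one sample of 30, and its size depends on assumed true change and B-CAM error. Another is that agreement would be only 68%. That figure arises when true responders gain exactly 4 points, which puts them on the cut and misclassifies half of them at any reliability below 1, so it says little about the C3Q. A third is that the plan treats low agreement as proof that self-report is unrelated to performance; it nowhere says so.

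**Conclusion.** The point holds as a minor one. The half-SD arithmetic is correct and the choice of cut is not the fault. What the plan lacks is a reference against which to read its only measure of concordance. With the stated SD and index, about 19% of unchanged people would be C3Q responders by error, or about 12-16% at an SD of 6-7 with reliability 0.84. Under an assumed B-CAM reliability of 0.84, agreement near 0.69 is expected both with no change at all and with perfect true concordance in 40% of people, while kappa goes from 0 to 0.38. An empty cell c would be rare even under perfect concordance: about 2% in the scenario worked above, and 5-10% at the smaller SDs. The sizes rest on normal independent errors, the internal index standing in for reliability, and the stated scenarios. The direction does not depend on the exact values.

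**What to change.** Keep the half-SD table and percent agreement with its 95% CI. In the same paragraph of STATISTICAL ANALYSIS AND SAMPLE SIZE, add:

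1. kappa with a 95% CI;
2. the correlation between continuous C3Q change and B-CAM change, with a 95% CI;
3. the number of C3Q responders expected from measurement error alone, computed as n × [1 − Φ(4 / (SD × √(2 × (1 − 0.84))))] with the baseline SD seen in the sample, and with a note that 0.84 is an internal index;
4. a sentence that neither the agreement level nor c = 0 will be interpreted without these references.

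The cost is a few lines of text and a little more analysis, with no new data. The plan should also state that kappa and the correlation are themselves attenuated by measurement error and imprecise at this size: with 30 people, an observed correlation of 0.43 has a 95% CI of about 0.08 to 0.68 (Fisher z, standard error 1/√27).
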